10.1.3 Figures of Concentration Versus Time Curves of Individual Subjects	
Population	: 
GTI1401:PK population GTI1401-OLE: Safety population

Contents	: 
GTI1401
 
For concentration data, serum alpha₁-PI concentration versus time curves following 8 weeks of treatments in individual subjects will be presented in one figure with the actual elapsed time from the start of the study drug infusion plotted on the x-axis.
 
GTI1401-OLE
 
Follow the same procedure, but use concentration prior to infusion in week 1 and all available visits on and after Ext Week 12.

10.1.4 Figures of Concentration Versus Time Curves of All Subjects	
Population	: GTI1401:PK population GTI1401-OLE: Safety population
Contents	: GTI1401 For all subjects combined, mean or median plasma alpha ₁ -PI concentration versus time curves following 8 weeks of treatments will be presented in one figure with the nominal time plotted on the x-axis. GTI1401-OLE Follow the same procedure, but use concentration prior to infusion in week 1 and all available visits on and after Ext Week 12.

All serum alpha₁-PI concentration vs. time curves will be plotted on both linear and semi-log scales.

A spaghetti plot (on the linear scale only) will be presented for all subjects following 8 weeks of treatment for concentration values vs nominal time.

Calculation of PK Parameters

The pharmacokinetic profiles of alpha₁-PI following weekly administration of Alpha-1 MP will be characterized by pharmacokinetic parameters, including area under the curve (AUC) at steady state following 8 weeks of weekly infusions (AUC_{0-7days}), maximum concentration (C_{max}), time to first observed maximum concentration (t_{max}), and half-life (t_{1/2}), based on alpha₁-PI concentrations in serum measured using content assay.

All PK parameters will be calculated using non-compartmental methods with WinNonlin software (Pharsight Corporation, Cary NC).

The pharmacokinetic parameters of interest are determined as follows:

AUC_{0-7days} area under the concentration vs. time curve at steady state over the weekly dosing interval (time 0 to 7 days), calculated by a combination of linear and logarithmic trapezoidal methods and expressed in the unit of concentration x time (mg·hr/dL). The linear trapezoidal method will be used for all incremental trapezoids arising from increasing concentrations and the logarithmic trapezoidal method will be used for those arising from decreasing concentrations.

C_{max} the first observed peak serum alpha₁-PI concentration following drug infusion obtained directly from the experimental data without interpolation, expressed in concentration units (mg/dL).

t_{max} the observed time to reach peak serum alpha₁-PI concentration obtained directly from the experimental data without interpolation,

expressed in time units (hour). If there are more than one maximum observed concentration, the t_{max} is the time to the first observed peak concentration.

$t_{1/2}$	the terminal half-life, calculated as $(\ln 2)/K_{el}$, expressed in time units (hour). The apparent terminal first-order elimination rate constant, determined by linear regression analysis of the natural log-linear segment of the plasma concentration-time curve, expressed in time ⁻¹ units (1/hour). At least 3 time points over 7 days following the treatment at week 8 will be included in the determination of K_{el} (Points prior to C_{max} or prior to the end of infusion are not used).
C_{min}	In GTI 1401 study, the observed serum concentrations prior to the start of infusions obtained at Weeks 7, 8 and at 7 days (168 hours) post infusion at Week 8, expressed in concentration units (mg/dL). In GTI 1401-OLE study use concentration prior to infusion obtained from all scheduled visits starting from Ext Week 12.
Mean C_{min}	the average trough concentration at steady state, calculated as the mean value using the three C_{min} measurements obtained. In GTI 1401 study use concentration obtained at Weeks 7, 8 and at 7 days (168 hours) post infusion at Week 9. In GTI1401-OLE study use concentration obtained value prior to infusion from all scheduled visits starting from Ext Week 12.

Analysis of PK Parameters

For PK parameters descriptive statistics and geometric mean (except t_{max}) will be calculated.

10.1.5 Summary of PK Parameters	
Population	:
Contents	PK population
For following PK parameters, descriptive statistics including n, mean, standard deviation (SD), %CV, median, minimum, maximum and geometric mean (except t_{max}) will be calculated. The digits to be displayed and units will be described in Table B.	
Data listing for PK parameter will be provided.	

Table B

Contents	Digits to be displayed
$AUC_{0-7\text{days}} [\text{mg} \cdot \text{hr/dL}]$	1 decimal place
$C_{max} [\text{mg/dL}]$	2 decimal place
$t_{max} [\text{hours}]$	2 decimal place
$t_{1/2} [\text{hours}]$	2 decimal place

Lung density

Subjects will undergo CT scanning for diagnosis of clinically apparent pulmonary emphysema in GTI1401 study. This CT scan data will also serve as the baseline measurement of lung density for GTI1401-OLE study. Lung density collected by the CT scan data will be summarized in Demographics (parameter name=both).

In GTI1401-OLE study, the CT scan will be performed and summarized at every 52 weeks (Annually) starting Ext Week 52.

The CT scan data will be accumulated for the future evaluation of lung density.

10.2.1 Summary Table of Lung Density	
Population	: Safety population
Contents	: For following parameters and locations, descriptive statistics of measured value and change from baseline are calculated. Descriptive Statistics including n, mean, standard deviation (SD), median, minimum and maximum. The digits to be displayed, units and all locations will be described in Table: Lung Density Parameter and Table: Target Locations. Data listing for Lung density parameters will be provided.

10.2.2 Figures of Lung Density Versus Time Curves of Individual Subjects (GTI1401-OLE only)	
Population	: Safety population
Contents	: For individual subject, Hu value 15 percentile [g/L] versus time plot will be presented using “Lung” as a target location in one figure using analysis visit (Annually) plotted on the x-axis.

10.2.3 Figures of Mean value of Lung Density Versus Time Curves of All Subjects (GTI1401-OLE only)	
Population	: Safety population
Contents	: Follow the same procedure as Figure 10.2.2 except plot mean Hu value 15 percentile [g/L] versus time plot using all subjects.

Table: Lung Density Parameter

Contents	Conversion formula for analysis value	Digits to be displayed
Hu value 15 percentile [g/L]	Original value [housfield unit] + 1000	1 decimal place
Mean [g/L]	Original value [housfield unit] + 1000	1 decimal place
Standard deviation [g/L]	Original value [g/L]	1 decimal place
Percent below -856 hu [%]	Original value	1 decimal place
Percent below -910 hu [%]	Original value	1 decimal place
Percent below -950 hu [%]	Original value	1 decimal place
Total volume in cm3 [mL]	Original value	1 decimal place
Air volume in cm3 [mL]	Original value	1 decimal place
Tissue volume in cm3 [mL]	Original value	1 decimal place

Table: Target Location

1	:	Lung
2	:	Lung, Left
3	:	Lung, Left Lower Lobe
4	:	Lung, Left Upper Lobe
5	:	Lung, Right
6	:	Lung, Right Lower Lobe
7	:	Lung, Right Middle Lobe
8	:	Lung, Right Upper Lobe
9	:	Lung, Thirds Left Lower
10	:	Lung, Thirds Left Middle
11	:	Lung, Thirds Left Upper
12	:	Lung, Thirds Right Lower
13	:	Lung, Thirds Right Middle
14	:	Lung, Thirds Right Upper

11 Safety Analysis

Adverse Events

Definition of Adverse Events

Adverse Event:	
An AE is any untoward medical occurrence in a subject or clinical investigation subject administered a pharmaceutical product, which does not necessarily have a causal relationship with this treatment.
 
An AE can therefore be any unfavorable and unintended sign (including an abnormal laboratory finding), symptom, or disease temporally associated with the use of a medicinal product, whether or not considered related to the IMP.
 
In this protocol, non-serious COPD exacerbation will not be considered as adverse events unless SAE.

TEAE for GTI 1401	
Treatment emergent adverse events (TEAE) for GTI 1401 will be defined as any adverse event occurred after or on the first study drug infusion of GTI 1401 to the final visit of GTI 1401.
 
For any subject, all AEs that occur at any time from the beginning of Alpha-1 MP administration until the final visit of the clinical trial will be considered as TEAE.
 
All tables regarding to Adverse Events are restricted to TEAE.

TEAE for GTI1401-OLE	
Treatment emergent adverse events (TEAE) for GTI 1401-OLE will be defined as any adverse event occurred after or on the first study drug infusion of GTI 1401-OLE to the final visit of GTI 1401-OLE or adverse event which continue from GTI 1401 to GTI 1401-OLE.
 
For any subject, all AEs that occur at any time from the beginning of Alpha-1 MP administration until the final visit of the clinical trial will be considered as TEAEs
 
All tables regarding to Adverse Events are restricted to TEAE.

Adverse Drug Reaction (ADR):	The phrase “responses to a medicinal product” means that a causal relationship between a medicinal product or study treatment and an AE is at least a reasonable possibility, that is, the relationship cannot be ruled out.

	
When an AE is classified, assessing causal relationship by the Investigator, as “definitive”, “probable”, “possible” or “doubtful/unlikely”, the event will be defined as a suspected ADR. When the causal relationship is labeled “Unrelated”, then it will be considered that the AE is not imputable to the study treatment and it is not a suspected ADR.

Serious Adverse Events (SAEs):	
Any event reported on the AE CRF form with the serious field ticked “Yes”.
 
A SAE is any untoward medical occurrence that at any dose:
 
Results in deathIs life-threatening 
Note: The term “life-threatening” in this definition refers to an event in which the subject is at risk of death at the time of the event; it does not refer to an event that hypothetically might cause death if it were more severe.
 
Requires inpatient hospitalization or prolongation of existing hospitalization
 
Results in persistent or significant disability/incapacity
 
Is a congenital anomaly/birth defect

Events of Special Interest:	
Events of special interest include the following:
 
All COPD exacerbations occurring during the study will be recorded. Each subject will be assessed for signs and symptoms of exacerbations at each study visit as specified in Appendix 1 and Appendix 2. Given that COPD exacerbations are part of the natural history of AATD, COPD exacerbations will not be reported as AEs unless a COPD exacerbation meets the criteria of a SAE. If an exacerbation meets criteria for a SAE, it will be reported as such, and the standard of care should be followed. Results from standard of care should be obtained and reported.

Adverse events with incomplete start dates will be considered treatment emergent (TEAE) if:

- Day and Month are missing and the year is equal to or after the year of the first study drug dose date of each study (1401/1401-OLE);
- Day is missing, month is present and the month is equal or after the month of first dose of each study (1401/1401-OLE) and the year is equal or after the year of first dose date of each study (1401/1401-OLE);
- Day is missing and the year is equal to the year of the first infusion date of each study (1401/1401-OLE) and the month is equal to or after the month of the first infusion date of each study (1401/1401-OLE);
- Complete date is missing.

The AE tables will include the number and percentage of subjects by MedDRA primary System Organ Classes (SOC) - sorted by alphabetical order, MedDRA Preferred Terms (PT) - sorted by alphabetical order. A subject with more than one occurrence of the same adverse event in a particular system organ class/preferred term will be counted only once in the total of those experiencing adverse events in that particular system organ class/preferred term.

If a subject experiences the same adverse event at more than one severity, or with more than one relationship to study drug, the most severe rating or the stronger causal relationship to study drug will be given precedence. Any missing severity/relationship will be accounted as “worst case” as related in the tables.

All AE tables will be provided without separating AE occurred during treatment period with Follow-up period.

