11.1.1 Overview of AEs		
Population	:	Safety population
Contents	:	
Overview AE table will be tabulated and will present number and percentages of subjects and number of events with following items.
 
• AEs• ADRs• AEs with fatal outcome• SAEs• AEs leading to premature discontinuation from the study• Events of special interest

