11.1.5 Summary Table of AEs by Severity**11.1.6 Summary Table of ADRs by Severity**

Population	:	Safety population
Contents	:	The number and percentage of incidences of AEs, and ADRs by severity based on SOC and PT will be summarized.

Following Listings regarding AEs will be provided.

- AEs
- SAEs
- Subjects with deaths
- AEs leading to premature discontinuation from the study
- AEs with Non-Serious COPD Exacerbation

Laboratory Tests

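### The extension study's TEAE definition carries over any ongoing adverse event without an onset limit, so an event that began before any Alpha-1 MP can be tabulated as treatment-emergent

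*SAP*

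**What the plan says.** Section 11 of the SAP (Adverse Events, Definition of Adverse Events) defines TEAEs separately for the two studies.

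- **GTI1401:** "any adverse event occurred after or on the first study drug infusion of GTI 1401 to the final visit of GTI 1401". Onset on or after the first infusion is required.
- **GTI1401-OLE, first sentence:** there are two routes. One is onset between the first extension infusion and the final extension visit. The other is "or adverse event which continue from GTI 1401 to GTI 1401-OLE".
- **Second sentence, in both definitions:** it counts as TEAEs "all AEs that occur at any time from the beginning of Alpha-1 MP administration until the final visit of the clinical trial".
- **Use of the flag:** "All tables regarding to Adverse Events are restricted to TEAE".

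The same section has a rule for partial dates, introduced by "Adverse events with incomplete start dates will be considered treatment emergent (TEAE) if". It compares what is known of the start date with the first dose of each study.

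Section 3.1 makes long-term safety the primary objective of the extension. Section 4.1 places a Screening Period of up to three weeks inside GTI1401 and makes Week 9 of GTI1401 the first week of the extension. In Appendix 1, Screening runs from Day -21 to the day before Week 1, and the adverse event row is marked at Screening.

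**The concern.** The carry-over route refers to adverse events, not to TEAEs, and sets no earliest onset. GTI1401 includes Screening, so an event that began in Screening is an event of GTI1401 and can continue into the extension. Under the GTI1401 rule it is not treatment-emergent, because it began before dosing. Under the extension rule the same event is treatment-emergent if it is still present at Ext Week 1.

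An event thus changes status by lasting, not by any relation in time to the start of Alpha-1 MP. Since all adverse event tables use this flag, the event would enter the extension's overview, SOC/PT, causality and severity tables. If its relationship to study drug were missing, the worst-case rule in sections 5.2 and 11 would also count it as related. These tables serve the extension's primary objective.

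A lesser point is an ambiguity in the second sentence of the extension definition. It does not say which study's first infusion marks the beginning of administration.

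Carrying forward events that began on Alpha-1 MP and are still ongoing is the SAP's convention and is not questioned here.

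**Working it through.** The SAP states no figure to reproduce; section 5.4 says there was no formal sample size calculation. The check applies each rule to the possible event histories of a subject who rolls over.

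**Time scale.** Day 0 is the first GTI1401 infusion (Week 1). Screening is day -21 to day -1 (Appendix 1). Ext Week 1 is Week 9, that is 8 × 7 = 56 days after Week 1, or 55 to 57 with the ±1 day visit window of section 5.3.2.

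**Classification**

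| Event history | GTI1401 TEAE | OLE, first sentence as written | OLE second sentence, read per study | OLE second sentence, read as first-ever infusion | OLE with onset limit |
|---|---|---|---|---|---|
| 1. Screening onset, resolved before dosing | no | no | no | no | no |
| 2. Screening onset, ongoing at Ext Week 1 | no | **yes** | no | no | **no** |
| 3. On-drug onset in GTI1401, resolved before Ext Week 1 | yes | no | no | yes | no |
| 4. On-drug onset in GTI1401, ongoing at Ext Week 1 | yes | yes | no | yes | yes |
| 5. Onset after the first extension infusion | no | yes | yes | yes | yes |

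The second sentence adds to the first and removes nothing:

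- Read per study, it adds nothing, and the extension set is histories 2, 4 and 5.
- Read as the first-ever infusion, it adds history 3, and the set becomes 2, 3, 4 and 5.
- History 2 is admitted on either reading.
- The onset limit, with the second sentence deleted or tied to each study, leaves 4 and 5.

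**Partial dates.** That rule applies only when the start date is incomplete. It does not touch a fully dated Screening event.

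**How long the event must last**

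- Onset the day before Week 1: 56 + 1 = 57 days (56 to 58 with the window).
- Onset on Day -21: 56 + 21 = 77 days (76 to 78 with the window).

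**Effect on a table row.** One added subject changes a row by 100/n percentage points, where n is the number of subjects in the extension tables. The SAP gives only a target of at least 3 for the study and not how many enter the extension, so n is assumed.

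| n (assumed) | Change in row (percentage points) |
|---|---|
| 3 | 100/3 = 33.3 |
| 4 | 100/4 = 25.0 |
| 5 | 100/5 = 20.0 |
| 6 | 100/6 = 16.7 |

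These are upper limits. A subject with repeated occurrences in the same SOC/PT "will be counted only once in the total of those experiencing adverse events", so the change is 0 if the subject is already in that row. The overview in section 11.1.1 "will present number and percentages of subjects and number of events with following items", so its event count rises by 1 in either case. These percentages concern history 2 only; none is claimed for the second-sentence ambiguity.

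**The case against.** Five points can be made for leaving the text alone.

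- **The general AE definition.** Section 11 ties an adverse event to a subject who has been given a product, so a pre-dose event is arguably not one. But Appendix 1 evaluates adverse events at Screening, and restricting the tables to TEAEs presupposes events that are not treatment-emergent. The general definition cannot carry the exclusion.
- **The second sentence signals the intent.** Read with the first, its reference to the beginning of Alpha-1 MP administration suggests that onset on drug is meant. A programmer might well read it so. It is worded as an inclusion, however, and excludes nothing.
- **Recording practice.** A pre-dose event might be recorded as medical history, and when recording of adverse events starts is often left to the protocol. This stands as a limit on how often the case will arise. It does not repair the rule.
- **The schedule table.** In the extracted text of Appendix 1, the infusion row shows seven marks against the eight infusions of section 4.1, so the table is not intact. Even so, rows not done at Screening, such as vital signs and infusion, begin with an empty cell, while the adverse event row begins with a mark.
- **Small consequence.** The rule can only over-include and cannot hide an event. There is no comparator or test. The 100/n figures would hold for any single event in a group this small. Onset can be checked in the listings: "Following Listings regarding AEs will be provided". All of this stands, and it is why the point is minor.

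**Conclusion.** The concern holds, as a minor one. Followed literally, the extension definition labels as treatment-emergent an event that began before any Alpha-1 MP, while the GTI1401 definition excludes the same event. Neither the second sentence, nor the partial-date rule, nor the general AE definition prevents this.

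The route is narrow, since only events lasting about 8 weeks or longer from a Screening onset qualify. When it occurs, the effect on one row is anywhere from none to 33.3 points with 3 subjects in the extension, and less with more, plus one event in the overview. This rests on two assumptions: that pre-dose events are recorded as adverse events at Screening, as the schedule indicates, and on the illustrative number of subjects entering the extension. No safety conclusion is shown to change. The second-sentence ambiguity is a wording matter of lesser weight.

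**What to change.** In the GTI1401-OLE definition, limit the carry-over route to events with onset on or after the first GTI1401 infusion, in other words GTI1401 TEAEs still ongoing at entry to the extension. Events that began on Alpha-1 MP and continue remain extension TEAEs, as the SAP intends; only Screening-onset events drop out. Delete the second sentence, or tie it explicitly to the first infusion of the respective study.

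The cost is one limiting clause and one sentence in the SAP, and one start-date condition in the program that sets the extension TEAE flag. No new data are needed.

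### The partial-date rule tests month and year separately, so some adverse events that certainly began after dosing are not counted as treatment-emergent

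*SAP*

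**What the plan says.** SAP section 11, under Adverse Events, gives four conditions under which an event with an incomplete start date counts as treatment-emergent. They are applied separately to GTI1401 and GTI1401-OLE.

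1. Year only known: "Day and Month are missing and the year is equal to or after the year of the first study drug dose date of each study".
2. Only the day unknown; the condition reads "month is present and the month is equal or after the month of first dose of each study (1401/1401-OLE) and the year is equal"; a year later than that of the first dose also satisfies the year part.
3. Only the day missing, same year: "Day is missing and the year is equal to the year of the first infusion date of each study", with the month again equal to or later than the first-infusion month.
4. No date at all: "Complete date is missing".

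The definitions earlier in section 11 count every event from the first administration to the final visit as treatment-emergent. For the OLE they add events continuing from GTI1401. They also state: "All tables regarding to Adverse Events are restricted to TEAE".

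**The concern.** Whether one month-and-year pair comes after another has to be judged on the pair, year first. Condition 2 compares the two parts independently and joins them with a logical and. That works within one calendar year but fails once follow-up passes into the next, because month numbers restart at 1.

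The result conflicts with the SAP's own definition of a treatment-emergent event. It also means that knowing more about a date can remove an event that would count if less were known.

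Safety is the primary objective of both studies (section 3.1), and the overview, AE, ADR, causality and severity tables (11.1.1 to 11.1.6) all rest on this classification. The OLE runs for about a year or longer, so passing into a new calendar year is normal there. The planned size is at least three subjects (section 5.4). At that minimum, losing one subject's only event of a given type changes its reported incidence from 1/3 = 33.3% to 0%.

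**Working it through.** The SAP states no figure on this point, so there is none to reproduce. The check applies the four conditions literally and compares them with calendar order.

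**Notation.** First dose in month M of year Y; event start in month m of year y, day unknown.

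- Condition 2: m ≥ M and y ≥ Y.
- Condition 3: y = Y and m ≥ M. Every case meeting this also meets condition 2, so it adds nothing.
- Correct test: y > Y, or (y = Y and m ≥ M).

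**Worked example (assumed dates).** First dose November 2017 (M = 11, Y = 2017); event in February 2018, day unknown (m = 2, y = 2018).

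| Condition | Test | Met? |
|---|---|---|
| 1 | requires month missing; month is known | no |
| 2 | 2 ≥ 11 is false | no |
| 3 | 2018 = 2017 is false | no |
| 4 | requires whole date missing | no |

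The event is not admitted. If only the year 2018 were known, condition 1 would give 2018 ≥ 2017 and admit it. With no date, condition 4 would admit it.

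**How many calendar months are affected.** In each later year the months numbered below M fail, which is M − 1 months. Over the 12 calendar months after the first-dose month:

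| First dose in | Months misclassified | Share of 12 |
|---|---|---|
| January | 0 | 0% |
| June | 5 | 42% |
| September | 8 | 67% |
| November | 10 | 83% |
| December | 11 | 92% |

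Summed over the 12 possible start months, 0 + 1 + … + 11 = 66 combinations of start month and event month are misclassified. The percentage depends on whether the first-dose month itself is in the denominator:

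- Without it: 66/(12 × 12) = 66/144 = 45.8%, and the same for two or three years.
- With it: 66/(12 × 13) = 66/156 = 42.3% for one year, 132/300 = 44.0% for two and 198/444 = 44.6% for three.

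**GTI1401.** From the Week 1 infusion to the 30-day follow-up is 7 × 7 + 30 = 79 days, so only starts late in the year reach January. Taking the first-dose month and the three months after it as the window, 6 of 12 × 4 = 48 combinations (12.5%) are misclassified, all for first doses in October to December.

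**Direction.** In the enumeration the literal rule never admitted a month before the first-dose month. The error only removes events. The correct test misses 0 of the 156 combinations and admits no pre-dose month.

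**The case against.** The strongest reply is that the list says if, not only if. The general definition already makes any event after first administration treatment-emergent, and February 2018 is plainly after November 2017, so a programmer could fall back on that definition. The SAP does not say so. A list of qualifying conditions has no function unless dates that match none of them fail, and coded as written it drops these events.

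Four further points limit the reach without removing the fault.

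- **Carry-over.** An event continuing from GTI1401 into the OLE still counts in the OLE. New events with onset in the OLE are not helped.
- **Two tests.** Each study has its own test, so an event missed for one may pass for the other. If the OLE starts two calendar months after GTI1401, 47 of 180 combinations (26.1%) over the 15 calendar months from the first GTI1401 dose are admitted by neither. Passing the other study's test is not a full remedy, because section 5 presents the two studies separately.
- **Listings.** The AE listings are not stated to be restricted to treatment-emergent events, so a lost event may be visible there. The incidence tables would still be wrong and would disagree with the listings.
- **Rarity.** Infusions are weekly and on site, so an unknown start day should be uncommon. The analysis is descriptive and no hypothesis test is affected. Both points stand.

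**Conclusion.** The concern holds. As written, the rule excludes events with an unknown start day that fall in a later year but an earlier month than the first dose. This contradicts the definition in the same section and the rule's own treatment of less complete dates. The error runs one way, towards lower incidence of AEs, ADRs and SAEs.

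For a first dose in month M it affects M − 1 months of each later calendar year. Averaged over equally likely start months, that is 42% to 46% of follow-up months in the OLE, depending on the denominator and the length of follow-up. In GTI1401 it affects only starts in October to December. These figures describe calendar months and rest on a literal reading of the four conditions. The number of events affected is unknown, probably small and possibly zero. With so few subjects, one lost event could still alter a table that serves the primary objective, so the rule should be corrected before the tables are produced.

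**What to change.** Replace conditions 2 and 3 with one: when the day is missing and month and year are present, the event is treatment-emergent if its year is later than the year of the first dose in the study concerned, or if the year is the same and its month is equal to or later than the month of that first dose. Keep conditions 1 and 4. State that the list is exhaustive for incomplete dates, so that no programmer has to guess whether the general definition applies as a fallback. If the sponsor also wants to exclude events whose known end date precedes the first dose, that can be added as a separate condition; this correction does not depend on it.

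The cost is one sentence of SAP text and one line of derivation code. No new data are needed.
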